7. STATISTICS AND DATA ANALYSIS

Approximately 350 participants have been identified. This includes people who attend the Imperial College Healthcare NHS Trust diabetes clinics, and people who have given the Imperial diabetes research team their consent to be contacted for research. Approximately 16 potential participants will be enrolled into the interview sub-study. This is based on the number estimated to be required to identify no new themes (i.e. reach saturation).

Of the participants who are enrolled into the study (and who have consented to be contacted for an interview) the research team plan to select approximately 16 whose HAS scores are relatively higher than other participants in order to conduct a qualitative semi-structured interview. This will be judged from previous research and participants who score in the upper quartile of the entire measure. (Singh *et al.*, 2014). Participants of varying backgrounds will be selected to ensure a mix of demographics, diabetes duration, HbA1c etc. This is in order to ensure a heterogeneous pool of participants to inform our hypothesis.

This study contains both descriptive and quantifiable data. The quantitative outcomes may be either ordinal or categorical, and proportions tests, including Chi squared tests, t-tests and ANOVAs will be used to determine differences between these outcomes.

The descriptive data will be tabulated and presented as such without statistical analysis. Interviews will be audio-recorded and transcribed verbatim. They will be analysed using a grounded theory approach (Corbin & Strauss, 1990), which aims to develop a set of concepts that provide a theoretical explanation of the phenomenon being studied. Analysis will take place alongside data collection, as it will inform and direct subsequent interviews. Credibility checks (Elliott, Fischer & Rennie, 1999; Stiles, 1993) will involve a third-party examining sections of analysed interview transcripts and providing feedback. In addition to this the researcher will contact the interview participant participants to check the themes with the interview participant and providing feedback.

All personal details will be sent via encrypted email (nhs.net).

Record linking participant information to study ID will be stored securely on an Imperial College NHS trust Computer. All study data will be stored in a pseudonymised format in an encrypted database on an Imperial College NHS trust computer OR Imperial College London computer.

Audio recordings will be recorded on a secure dictaphone in pseudonymised form and once transcribed will be destroyed. All transcribed data will be stored on an ICHT or ICL computer in pseudonymous form.

Direct quotations may be published in anonymous fashion. The NHS Code of Confidentiality will be followed at all times. All data is to be stored in a pseudonymised form by using study codes for de-identification of participants. Examples of such a code includes: HYPE001 (assigned in order of enrolment). Identifiable Personal data will be kept in files in a locked office within Imperial College London, accessible only by the research/clinical team. Pseudonymised data will be stored in a password encrypted spreadsheet on ICHT/ICL computers, accessible only by the research team.

Data and all appropriate documentation will be pseudonymised and stored for a minimum of 10 years after the completion of the study in line with Imperial College policy.

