1. INTRODUCTION

1.1 Background

Approximately 400000 people in the UK have T1D (1). Self-management of T1D involves a challenging regimen requiring monitoring of blood glucose levels several times per day and multiple daily insulin injections. People living with T1D can experience a number of psychological difficulties, including feeling burned out, fear of high and low blood glucose levels, adjustment to diabetes-related complications, and problems around eating. Higher levels of diabetes-related distress are associated with a higher HbA1c (2,3) which is associated with increased risk of micro- and macro vascular diabetes-specific complications. The importance of psychological support for people with T1D is increasingly recognised (4), and both published and Imperial data demonstrate the importance of psychological support (5,6).

Published data describe the assessment and consequences of fear of hypoglycaemia in people with T1D (7,8). Hypoglycaemia fear is associated with a higher HbA1c and increased risk of diabetes-related complications. The Hypoglycaemia Fear Survey (HFS-ii) (9,10) is a valid and reliable tool for assessment used in routine clinical care, including in the psychological assessment and intervention outcome data for the Imperial T1D Psychology service. NICE guidelines (11) reference fear of hypoglycaemia as a barrier to achieving HbA1c targets and recommend continuous glucose monitoring for those with extreme fear.

There is, however, little research about fear, or problematic avoidance, of hyperglycaemia in T1D (12). It is, however, a problem that we see in the T1D clinics at Imperial, often with significant adverse consequences. As well as high levels of distress, it is associated with recurrent hypoglycaemia exposure, eroded hypoglycaemia awareness and increased healthcare utilisation (13). More problematically, fear of hyperglycaemia may not be identified, as the HbA1c is often at, or below, target.

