2. STUDY OBJECTIVES

Primary Objective

Assess how problematic fear of hyperglycaemia is in T1D

Secondary Objectives

Identify whether fear of hyperglycaemia is associated with any clinical factors

Identify the psychological factors that underpin fear of hyperglycaemia

Assess how fear of hyperglycaemia affects self-management of T1D

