3. STUDY DESIGN

Non-interventional, cross-sectional questionnaire study in adults with T1D

1 hour per participant, 9 months total

n=up to 350 participants total

Sub study of approximately n=16 participants for semi-structured interviews (1.5 hours per participant)

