3.1 Study Outcome Measures

1. Quantitative data:

- a. Hyperglycaemia avoidance scale (HAS)
- b. Hypoglycaemia fear survey (HFS-II)
- c. Problem areas in diabetes scale 5 (PAID-5)
- d. Patient health questionnaire (PHQ-9)
- e. Generalised anxiety disorder scale (GAD-7)
- f. State trait anxiety inventory (Trait subscale)

2. Descriptive data – semi-structured interview

Additional baseline participant data to be pulled from Cerner/via participant survey:

- Age
- Ethnicity
- Length of diabetes
- Current diabetes treatment
- Diabetes complications: nephropathy, neuropathy, retinopathy, cardiovascular disease
- Recent HbA1C
- Other medical conditions
- Other medications
- Hypos – frequency/severity
- Blood glucose monitoring - method and frequency

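### Section 7 names only group-difference tests, although the secondary objectives relate the Hyperglycaemia Avoidance Scale to mostly numeric factors; correlation and regression should be added

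*Combined protocol and SAP*

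**What the plan says.** Section 7 gives the quantitative methods in a single sentence. On the type of data: "The quantitative outcomes may be either ordinal or categorical". On the tests: "proportions tests, including Chi squared tests, t-tests and ANOVAs will be used to determine differences between these outcomes". It does not say which groups are compared or which test serves which objective, and it does not claim that the list is complete. No section mentions correlation, regression or any other model of association.

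Section 2 sets the primary objective, "Assess how problematic fear of hyperglycaemia is in T1D", and three secondary ones. Two of these ask about relationships: "Identify whether fear of hyperglycaemia is associated with any clinical factors" and "Identify the psychological factors that underpin fear of hyperglycaemia". The third concerns the effect on self-management.

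Section 3.1 lists HAS, five other psychological scales (HFS-II, PAID-5, PHQ-9, GAD-7, trait anxiety) and ten baseline items. Section 6 shows that PHQ-9 runs up to 27 and GAD-7 up to 21. It also says, about letters reporting scores to participants, that some measures have no standard cut-off. Section 10 promises only descriptive summaries (mean or median, and spread). Section 3 gives the size as "n=up to 350 participants total".

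**The concern.** The objectives are about association, and the factors are largely scores or measurements. A t-test or ANOVA can relate HAS to HbA1c or to trait anxiety only if one of the two is first cut into groups. A chi-squared test needs both cut. Cutting a numeric score discards information, so modest associations are missed more often. Because the plan states no cut, one could also be chosen after the data are seen.

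The protocol's own background treats such relations as graded: "Higher levels of diabetes-related distress are associated with a higher HbA1c". That sentence reports literature on distress, not HAS, but it shows the form of the question. The label in section 7 also fits poorly with the tests beside it, since t-tests and ANOVA compare means of a numeric outcome.

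A smaller point is that HAS is never named as the primary measure and no confidence interval is mentioned for it. Section 10 can be read to cover its basic summary.

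**Working it through.** **No planned figure to reproduce.** The plan gives no alpha, effect size, cut or response rate. The 350 is the number of people identified (section 7) and a ceiling (section 3). The power figures below are therefore illustrations.

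**Step 1: count the factors in section 3.1.**
- Psychological scales other than HAS: 5, all giving scores.
- Baseline items that are clearly numeric: age, diabetes duration, HbA1c (3).
- Mixed items: hypoglycaemia frequency/severity, and monitoring method/frequency (2).
- Categorical or free text: ethnicity, treatment, complications, other conditions, other medications (5).

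Clearly numeric: 5 + 3 = 8 of 15. With the two frequency items: 10 of 15.

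**Step 2: formulas.** Assumptions: two-sided alpha 0.05, bivariate normal scores, and n = 350 or n = 175 (a 50% return).
- Both scores numeric (Pearson): power = Φ(atanh(r)·√(n−3) − 1.96).
- One score cut so that a share p lies above the cut at normal quantile q: replace r by r·φ(q)/√(p(1−p)). The multiplier is √(2/π) = 0.798 for a median split and 0.734 for an upper-quartile split. Squared, these give the share of information kept: 0.637 and 0.539. For cuts leaving 10% or 5% above, the share is 0.342 or 0.224.
- Both scores median-split: replace r by (2/π)·asin(r), which keeps about 0.41.

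**Step 3: one case in full (n = 350, r = 0.15; √347 = 18.63).**
- Numeric: 0.1511 × 18.63 − 1.96 = 0.855; Φ = 0.804.
- One median split: r becomes 0.1197; 0.1203 × 18.63 − 1.96 = 0.280; Φ = 0.610.
- HAS upper-quartile split: r becomes 0.1101; 0.1105 × 18.63 − 1.96 = 0.099; Φ = 0.539.
- Both median-split: r becomes 0.0959; 0.0962 × 18.63 − 1.96 = −0.169; Φ = 0.433.

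**Step 4: power across cases.** Spearman and four-band ANOVA (assumed shares 45/25/20/10%) are simulated.

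| n | r | Pearson | Spearman | One median split | HAS upper quartile | Both median-split | 10% cut | 5% cut | Four-band ANOVA |
|---|---|---|---|---|---|---|---|---|---|
| 350 | 0.15 | 0.804 | 0.774 | 0.610 | 0.539 | 0.433 | 0.374 | 0.263 | 0.560 |
| 350 | 0.20 | 0.965 | 0.944 | 0.850 | 0.786 | 0.670 | 0.591 | 0.424 | 0.826 |
| 350 | 0.30 | 1.000 | 1.000 | 0.995 | 0.986 | 0.955 | 0.910 | 0.759 | 0.997 |
| 175 | 0.15 | 0.509 | 0.480 | 0.351 | 0.305 | 0.243 | 0.211 | 0.154 | 0.291 |
| 175 | 0.20 | 0.758 | 0.710 | 0.560 | 0.492 | 0.394 | 0.338 | 0.238 | 0.488 |
| 175 | 0.30 | 0.982 | 0.970 | 0.893 | 0.835 | 0.731 | 0.643 | 0.466 | 0.877 |

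The 10% and 5% columns stand for a cut at a severe range such as those in section 6; the shares are assumed.

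**Step 5: check.** A 10,000-run simulation at n = 350, r = 0.15 gave 0.812, 0.618, 0.546, 0.461 and 0.380 for Pearson, one median split, HAS upper quartile, both median-split and 10% cut. The formula for two median splits is thus about 3 points pessimistic here; the others agree within about 1 point.

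**Step 6: where the loss becomes minor.** For 95% power after one median split, r = tanh((1.96 + 1.645)/√(n−3))/0.798. This is about 0.24 at n = 350 and 0.34 at n = 175.

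**The case against.** The strongest reply is that the harm is conditional. The list is not said to be exhaustive, no cut is proposed, and correlations can still be run on the same data. The severe ranges in section 6 trigger letters to GPs, and the upper quarter of HAS selects interviewees; neither is an analysis group. All of this is true, and the power figures must be read in that light. But the sentence is the only statement of inferential method, and it omits the ordinary tool for two stated objectives.

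Second, the loss depends on the cut. A t-test of the outer thirds of one score loses only a few points against Spearman: 71% against about 77% at n = 350, r = 0.15, and 66% against 72% at n = 175, r = 0.20. A three-group ANOVA on thirds, however, falls to about 61% in the first case, no better than a median split. Nothing in the plan points to the efficient choice.

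Third, among clinical factors alone only 3 to 5 of 10 are numeric. That stands. The named tests suit treatment, complications, ethnicity and monitoring method, so the remedy adds methods and does not replace them. The description of the factors as mostly numeric holds for all 15 together, and for every psychological scale. The self-management objective may be met partly by the interviews; the documents do not say.

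**Conclusion.** The concern holds. Followed as written, section 7 can relate HAS to at least 8 of the 15 listed factors only by grouping a score, with no cut stated. That mismatch does not depend on any assumed number.

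Its cost does. For weak associations (r = 0.15 to 0.20), splitting one score at the median takes about 12 to 20 points of power from a Pearson correlation, and about 9 to 16 points from Spearman. More extreme cuts, or cutting both scores, cost more. For r = 0.30 at full return, median splits cost at most about 5 points. These figures rest on an assumed alpha of 0.05, normal scores and, at n = 175, an assumed 50% return.

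This should be fixed before analysis. It does not threaten the study's data or its descriptive results.

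**What to change.** Reword the sentence in section 7:

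1. Describe the scale scores, age, diabetes duration and HbA1c as numeric, and keep them so. Relate each to the HAS total with a Spearman correlation and 95% confidence interval, and with a linear regression of HAS.
2. Keep t-tests and ANOVA for HAS across natural groups, and chi-squared tests for pairs of categorical items.
3. Name the HAS total as the primary measure and report its mean or median, SD and 95% confidence interval. The half-width for the mean would be about 0.105 SD at n = 350 and 0.149 SD at n = 175. Do not present the sample's own upper quartile as a prevalence, since it is about 25% by construction.
4. Word questionnaire results as associations, since the design is cross-sectional. Multivariable models are optional. The anxiety, depression and distress scales probably overlap, so if models are used, show unadjusted results alongside.

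The cost is a change of wording and a little more analysis, with no new data. Spearman gives up to about 5 points less power than Pearson when scores are normal, and linear regression assumes a roughly straight-line relation. Group means by published bands are easier to read clinically and can still be shown descriptively.

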8. REGULATORY ISSUES

8.1 Ethics approval

The Study Coordination Centre has obtained approval from the Cornwall and Plymouth Research Ethics Committee (REC) and Health Regulator Authority (HRA). The study must also receive confirmation of capacity and capability from each participating NHS Trust before accepting participants into the study or any research activity is carried out. The study will be conducted in accordance with the recommendations for physicians involved in research on human subjects adopted by the 18th World Medical Assembly, Helsinki 1964 and later revisions.

8.2 Consent

Consent to enter the study must be sought from each participant only after a full explanation has been given, an information leaflet offered, and time allowed for consideration. Signed participant consent should be obtained. The right of the participant to refuse to participate without giving reasons must be respected. After the participant has entered the study the clinician remains free to give alternative treatment to that specified in the protocol at any stage if he/she feels it is in the participant's best interest, but the reasons for doing so should be recorded. In these cases, the participants remain within the study for the purposes of follow-up and data analysis. All participants are free to withdraw at any time from the protocol treatment without giving reasons and without prejudicing further treatment.

8.3 Confidentiality

Anonymised quotes may be used in publications if the participant has given written informed consent. The Chief Investigator will preserve the confidentiality of participants taking part in the study and is registered under the Data Protection Act.

8.4 Indemnity

Imperial College London holds negligent harm and non-negligent harm insurance policies which apply to this study.

8.5 Sponsor

Imperial College London will act as the main Sponsor for this study. Delegated responsibilities will be assigned to the NHS trusts taking part in this study.

8.6 Funding

The study is funded by the Imperial Health Charity. No payments will be made to participants or investigators in this study.

8.7 Audits

The study may be subject to inspection and audit by Imperial College London under their remit as sponsor and other regulatory bodies to ensure adherence to GCP and the UK Policy Framework for Health and Social Care Research.

9. STUDY MANAGEMENT

The day-to-day management of the study will be co-ordinated through [name].

10. PUBLICATION POLICY

The study will be registered on the clinicaltrials.gov system and results will be disseminated by peer reviewed scientific journals, internal report, conference presentation and publication on websites. No identifiable personal data will be published. Anonymised quotes may be included in publications if the participant has given informed written consent. All anthropometry and personal clinical data will be expressed as mean/ median and spread of the population in the study. All participants will be informed of the results by letter at the conclusion of the study and details of any publications that arise from the study will be disseminated to participants.

12. APPENDICES

Appendix 1. Study Questionnaires (attached separately)

- Hyperglycaemia avoidance scale (HAS)
- Hypoglycaemia fear survey (HFS-II)
- Problem areas in diabetes scale 5 (PAID-5)
- Patient health questionnaire (PHQ-9)
- Generalised anxiety disorder scale (GAD-7)
- State trait anxiety inventory (Trait subscale)
- semi-structured interview

Appendix 2. Data Flow Mapping
